6.2 Concomitant Medication/Therapy

Any prior or concomitant therapy or medication given to a subject within 6 months prior to screening or during the study will be indicated on the eCRF. Dose and generic name or tradename will be indicated.

The following concomitant therapies or medications will not be permitted during the study:

- GnRH agonists other than the IMP.
- Other hormonal treatments (for example oestrogens, progestogens, danazol, gerstrinone, cyproterone acetate, and non-barrier contraception, etc).
- Surgery.
- Any concomitant therapies which, in the investigator's opinion, may interfere with the evaluation of study treatment efficacy and safety.
- Any experimental drug or device other than the IMP.

- Traditional Chinese medicine for the treatment of endometriosis.

As the primary endpoint will be assessed at Week 12, "add back" treatment will not be permitted before that time. If "add back" treatment is needed, according to the investigator's judgement, it can be initiated after the primary endpoint evaluation at Week 12. The reason for and date/time of all doses of "add back" treatment will be recorded in the eCRF. "Add back" treatment is recommended to be, but not limited to, tibolone at a dose of 2.5 mg once daily.

6.3 Procedures for Monitoring Subject Compliance

The investigator will be responsible for monitoring subject compliance. Subjects can be withdrawn from the study at any time if the investigator or the sponsor determines that the subject is not in compliance with the study protocol.

For this study, all doses of IMP will be administered to the subjects at the study centre by study site staff. Administration of IMP must occur at the study day indicated ± 3 days. Administration compliance will be assessed by comparing the number of doses expected with the number of doses administered. Any missing injection at Visits 2, 3 or 4 (Day 1, Week 4 or Week 8) will be regarded as a major protocol violation.

Where a subject is consistently noncompliant with IMP intake they should be discontinued from IMP/withdrawn from the study. Please refer to Section 4.3 for the criteria for discontinuing the subject from IMP.

7 ASSESSMENT OF EFFICACY

For the timing of assessments in this study, refer to the schedule in [Table 2](#).

7.1 Primary Efficacy Endpoint and Evaluation

The primary efficacy endpoint is the percentage of subjects castrated ($E_2 \leq 184$ pmol/L or 50 pg/mL) at Week 12. The primary endpoint will be evaluated based on centralised bioanalysis of serum samples for E_2 .

7.2 Secondary and Exploratory Efficacy Endpoints and Evaluations

Secondary and exploratory efficacy endpoints and evaluations are summarised in [Table 7](#).

Table 7 Secondary and Exploratory Efficacy Endpoints and Evaluations

Measure	Timepoint	Variable	Endpoint
E ₂ concentration	Baseline, Weeks 4, 8, 12 and 24	Castration rate (percentage of subjects with E ₂ below castration levels) E ₂ concentration	Secondary endpoints Percentage of subjects castrated (E ₂ ≤184 pmol/L or 50 pg/mL) at Weeks 4 and 8. Percentage of subjects castrated (E ₂ ≤110 pmol/L or 30 pg/mL) at Weeks 4, 8 and 12. E ₂ concentration at Weeks 4, 8 and 12. Exploratory endpoints Percentage of subjects castrated (E ₂ ≤184 pmol/L or 50 pg/mL) at Week 24. Percentage of subjects castrated (E ₂ ≤110 pmol/L or 30 pg/mL) at Week 24. E ₂ concentration at Week 24.
Endometriosis-associated pelvic pain (by 10 cm VAS)	Baseline, Weeks 4, 8, 12, 16, 20, 24 and end of study/early withdrawal	Change in endometriosis-associated pelvic pain	Secondary endpoint Change in endometriosis-associated pelvic pain (by 10 cm VAS) at Weeks 4, 8 and 12 compared to baseline. Exploratory endpoint Change in endometriosis-associated pelvic pain (by 10 cm VAS) at Weeks 16, 20, 24 and the end of study visit compared to baseline.
FSH and LH concentrations	Baseline, Weeks 4, 8, 12 and 24	FSH concentration LH concentration	Secondary endpoint FSH and LH concentrations at Weeks 4, 8 and 12. Exploratory endpoint FSH and LH concentrations at Week 24.
Menses recovery	Baseline, date of first observation of menstrual bleeding at Weeks 28, 32, 36 and end of study/early withdrawal	Time to menses recovery	Secondary endpoint Time to menses recovery.

E₂=oestradiol; FSH=follicle stimulating hormone; LH=luteinising hormone; VAS=visual analogue scale.

7.3 Methods and Timing of Assessing, Recording, and Analysing Efficacy Data

The methods for assessing efficacy data are described below, and the timing of efficacy assessments is discussed in Section 5. Procedures for recording efficacy data are discussed in Section 14.1, and methods of analyses are discussed in Section 10.4.6.

7.3.1 *Oestradiol, Follicle Stimulating Hormone and Luteinising Hormone Concentrations*

Assessments of serum E₂, FSH and LH concentrations will be performed at study visits at Day 1 (baseline) and Weeks 4, 8, 12 and 24, in accordance with Table 2. A further assessment will be conducted at Week 40 in subjects whose menses have not recovered by this timepoint. This assessment is considered a safety assessment, and is discussed in Section 8.2.5. In addition, serum E₂, FSH and LH concentrations will also be determined at Weeks 1, 2, 3 and 32 for subjects in the full PK/PD subgroup, as described in Section 9.2. All E₂, FSH and LH concentrations will be evaluated by the central laboratory.

7.3.1.1 *Oestradiol Concentrations*

Measurement of serum E₂ concentrations will be performed in a central laboratory in accordance with Good Laboratory Practice (GLP). All details of the sample collection, handling, shipment, methodology and reference ranges will be provided in the Study Manual and archived in the trial master file (TMF).

Castration rate will be assessed using a cutoff E₂ concentration of 184 pmol/L (50 pg/mL) for the primary and secondary efficacy endpoints, and 110 pmol/L (30 pg/mL) for the secondary efficacy endpoint only.

7.3.1.2 *Luteinising Hormone and Follicle Stimulating Hormone Concentrations*

Measurement of serum LH and FSH concentrations will be performed in a central laboratory in accordance with GLP. All details of the sample collection, handling, shipment, methodology and reference ranges will be provided in the Study Manual and archived in the TMF.

7.3.2 *Endometriosis-associated Pelvic Pain*

The severity of endometriosis-associated pain will be assessed by the subject at Day 1 (baseline), Weeks 4, 8, 12, 16, 20, 24, and at the end of study visit using a 10 cm VAS. Subjects will be asked to assess their most severe endometriosis-associated pain over the preceding 4 weeks. For the Day 1 (baseline) assessment, if subjects had undergone endometriotic surgery within the previous 4 weeks, they will be asked to assess their most severe endometriosis-associated pain postsurgery. The VAS to be used is presented in Appendix 1.

7.3.3 *Recovery of Menses*

Status of menses recovery will be assessed at all study visits, including the follow-up period (Weeks 28, 32, 36 and at the end of study visit). The date of menses (if available) will be recorded at the end of study visit. Time to menses recovery will be defined as the time (in days) between the date of the last dose of study drug and the date of the first day that the subject observed menstrual bleeding of the next menses period. Any subjects withdrawing from the study without menstrual bleeding will be censored in this analysis at the date of withdrawal. Any subjects without menstrual bleeding prior to the end of study visit will be censored in this analysis at the date of the end of study visit.

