5.2.3 Procedures during Study Treatment (Visit 2 Postdose to Visit 8)

Subjects receiving triptorelin acetate PR 1-month will receive study drug at each visit during the treatment period up to and including Visit 7 (Week 20, Day 141±3). Subjects receiving triptorelin pamoate PR 3-month will receive study drug at Visit 2 (Day 1) and Visit 5 (Week 12, Day 85±3) only.

The following procedures will be performed on all subjects at Visit 3 (Week 4, Day 29±3) and Visit 4 (Week 8, Day 57±3):

- Efficacy assessments (E₂, LH and FSH concentrations (samples taken predose for subjects receiving triptorelin acetate PR 1-month); VAS)
- Samples taken for sparse PK analysis (samples taken predose for subjects receiving triptorelin acetate PR 1-month)
- Vital signs
- Review of AEs

- New or changed concomitant medications/therapies
- Review of menses status and record date of menses onset (if applicable)
- Injection of IMP (subjects receiving triptorelin acetate PR 1-month only)

The following procedures will be performed at Visit 5 (Week 12, Day 85±3):

- Efficacy assessments (E₂, LH and FSH concentrations (samples taken predose for all subjects); VAS)
- Samples taken for sparse PK analysis (samples taken predose for all subjects)
- Physical examination
- Pelvic examination
- Vital signs
- Laboratory safety tests (blood sampling for biochemistry, haematology and urinalysis)
- 12-lead ECG
- Pelvic type B ultrasound scan (optional based on subject's disease condition, as judged by the investigator)
- Review of AEs
- New or changed concomitant medications, including details of any "add back" therapy
- Review of menses status and record date of menses onset (if applicable)
- Injection of IMP (all subjects)

The following procedures will be performed at Visit 6 (Week 16, Day 113±3) and Visit 7 (Week 20, Day 141±3):

- VAS assessment
- Vital signs
- Review of AEs
- New or changed concomitant medications/therapies, including details of any "add back" therapy
- Review of menses status and record date of menses onset (if applicable)
- Injection of IMP (subjects receiving triptorelin acetate PR 1-month only)

The following procedures will be performed at Visit 8 (Week 24, Day 169±3):

- Efficacy assessments (E₂, LH and FSH concentrations; VAS)
- Physical examination
- Pelvic examination
- Vital signs
- Laboratory safety tests (blood sampling for biochemistry, haematology and urinalysis)
- 12-lead ECG
- Pelvic type B ultrasound scan
- Samples taken for sparse PK analysis

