Serum E₂, FSH and LH concentrations and change from baseline will be summarised at each time point, using descriptive statistics (n, mean, median, SD and minimum and maximum values) and the 95% CI for the difference between treatment groups in mean concentration values and mean change from baseline values will be presented for each parameter.

The 95% CI for the difference in mean and change from baseline values are calculated using a linear model for repeated measurements adjusting for baseline value and its interaction with visit, treatment group and its interaction with visit, and randomisation stratification factors (endometriotic surgical history and the severity of endometriosis-associated pelvic pain at baseline) and its interaction with treatment group. In a case where the stratification factor recorded in the eCRF and IWRS are inconsistent, the eCRF data will be retained. Baseline and its interaction with visit will be added in the above SAS code.

Time to Menses Recovery:

Time to menses recovery will be defined as the time (in days) between date of last dose of study drug and date of first day the subject observed menstrual bleeding of the next menstrual period. Any subjects withdrawing from the study without menstrual bleeding will be censored in the analysis at the date of withdrawal, and any subjects without menstrual bleeding prior to the end of study visit will be censored in this analysis at the date of the last known menses status study visit. Any subjects who doesn't stop menses during the treatment duration (V2 till V8) are excluded this analysis. "Stop menses" is considered as at least one answer "No" for the question "Is the menses recovered since last visit" in CRF page "Status of Menses" at least 2 consecutive menses stop during treatment duration (V2 till V8).

Statistical Analysis Plan

Version: Final 3.1

Ipsen Pharma; Protocol No. D-CN-52014-220

Date of Issue: 13DEC2019

CCI

The number and percentage of subjects with menses recovery and censored subjects and their censor reasons will be summarised. The median time, 25th and 75th quartile times and their 95% CIs will be estimated using the Kaplan-Meier method; Kaplan-Meier curves will be plotted.

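### Time to menses recovery has no end-of-treatment bound, so menses during treatment can count as recovery over about 84 days in the 3-month arm but only 28 in the 1-month arm

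*Protocol*

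**What the plan says.** **Definition.** Protocol 7.3.3 starts the clock at the last dose and stops it at "the date of the first day that the subject observed menstrual bleeding of the next menses period". Protocol 10.4.6.2 and SAP 7.6.2 repeat the rule; the SAP measures between "date of last dose of study drug and date of first day the subject observed menstrual bleeding of the next menstrual period". No version sets an earliest date for the event.

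**Dosing.** Under Protocol 5.2.3 the 3-month arm is injected at "Visit 2 (Day 1) and Visit 5 (Week 12, Day 85±3) only". The 1-month arm is injected at each visit "up to and including Visit 7 (Week 20, Day 141±3"). Treatment ends in both arms at Week 24, Day 169±3.

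**Data collected.** Menses status is reviewed at every visit, and onset dates are recorded during treatment as well as in follow-up (Protocol 5.2.3 and 7.3.3).

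**Text pointing to recovery after treatment.** Table 7 in Protocol 7.2 gives, after baseline, the "date of first observation of menstrual bleeding at Weeks 28, 32, 36 and end of study/early withdrawal". Protocol 5.2.4 says that the follow-up period exists to monitor menses recovery.

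**SAP exclusion.** SAP 7.6.2 leaves out women whose menses did not stop during Visits 2 to 8. Stopping is judged from the menses-status page of the CRF and requires at least two consecutive stops within that span.

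**Analysis.** The summary is Kaplan-Meier by arm. The protocol asks for the median with its CI, and the SAP adds both quartiles. No between-arm test is planned.

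**The concern.** The arms have different last-dose days but the same end of treatment. An event rule tied only to the last dose therefore opens the clock eight weeks earlier in the 3-month arm, while those women are still under treatment. The same menses on the same study day can be an event in one arm and not in the other.

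The curve would then mix two things: loss of menstrual suppression during treatment, and return of menses after it. The mixture would differ by arm because of the injection schedule alone. A reader comparing the curves could take the difference for a property of the formulation.

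Add-back treatment adds uncertainty. Protocol 6.2 says "it can be initiated after the primary endpoint evaluation at Week 12", which is when the 3-month clock opens, and the endpoint definition does not say how bleeding under add-back is to be classified.

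**Working it through.** The plan gives no figure for this endpoint's event window or for on-treatment bleeding, so there is no plan figure to reproduce. The windows follow from the visit schedule.

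**Step 1. Inputs (Protocol 5.2.3 and 5.2.4).** Last dose: Day 85±3 (3-month) and Day 141±3 (1-month). End of treatment: Day 169±3. Latest end-of-study visit: Day 281±3.

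**Step 2. On-treatment time during which menses can be an event.**

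| | 3-month | 1-month |
|---|---|---|
| Last dose to Week 24 | 169 − 85 = 84 days | 169 − 141 = 28 days |
| Shortest with visit windows | 166 − 88 = 78 | 166 − 144 = 22 |
| Longest with visit windows | 172 − 82 = 90 | 172 − 138 = 34 |
| Last dose to Week 40 | 281 − 85 = 196 | 281 − 141 = 140 |

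These apply to women who are dosed on schedule to the end.

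**Step 3. One menses, two results.** Take menses starting on Day 127.
- 3-month arm: recovery is scored at 127 − 85 = 42 days, which is 169 − 127 = 42 days before treatment ends.
- 1-month arm: the menses come 141 − 127 = 14 days before the last dose, so they cannot be an event and the woman stays at risk.

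**Step 4. Does the SAP exclusion remove this?** No. The two consecutive stops may fall anywhere from Visit 2 to Visit 8. A woman without menses at Weeks 4 and 8 who bleeds before Week 16 meets the requirement and is kept. Her menses are an event only if she is in the 3-month arm. The exclusion removes women who never stopped, not those who stopped and bled again.

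**Step 5. Size.** Assume the same probability q of menses per 28 days of treatment in both arms, and ignore the exclusion. The 3-month window holds three 28-day periods and the 1-month window holds one:

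- share scored as recovered by Day 169, 3-month = 1 − (1 − q)³
- share scored as recovered by Day 169, 1-month = q

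| q (assumed) | 3-month | 1-month |
|---|---|---|
| 2% | 1 − 0.98³ = 5.9% | 2% |
| 5% | 1 − 0.95³ = 14.3% | 5% |
| 10% | 1 − 0.90³ = 27.1% | 10% |

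**Step 6. Effect on the reported summaries.** Early events act most on the lower quartile. On the same assumptions and without censoring, it falls inside the treatment period once 1 − (1 − q)³ reaches 0.25, that is q = 1 − 0.75^(1/3) = 9.1%. In the 1-month arm this needs q = 25%.

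**The case against.** The strongest reply is that the protocol, read as a whole, already places recovery after Week 24. Table 7 lists post-treatment contacts, Protocol 5.2.4 gives follow-up the task of monitoring recovery, and the end-of-study visit is due within 15 days of recovery. If menses on Day 127 were recovery, that visit would be due by Day 127 + 15 = 142, before Week 24, which does not fit the 24-week schedule. This is good evidence of intent. It does not settle the analysis, because the SAP rule to be programmed contains no such limit. Table 7 also includes early withdrawal, which can come before Week 24.

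Two stronger readings are tempting, and the documents support neither.

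- *Any bleeding after the last dose counts, including breakthrough or add-back bleeding.* The text refers to bleeding of the next menses or menstrual period. It does not separate this from spotting or add-back bleeding, which is a gap in definition, but it does not say that every bleed is an event.
- *A woman scored as recovered during treatment leaves follow-up, so her true recovery is lost.* Protocol 3.1 does end follow-up at recovery. However, visits to Week 24 apply to everyone, and Protocol 5.2.4 ties the final visit to recovery during follow-up. Loss of the later date is not shown.

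It is also fair to say that the percentages rest on assumed rates and that the ratio between arms mainly restates 84 against 28 days. Protocol 1.3 reports 97% and 94% castrated at Week 12 in the earlier European study, which makes the highest rate look less likely, though those figures say nothing about bleeding under add-back treatment.

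**Conclusion.** The point holds as an unbounded event definition that treats the arms unequally. Followed as written, SAP 7.6.2 allows menses during treatment to count as recovery over about 84 days in the 3-month arm and 28 days in the 1-month arm, among women who remain after the exclusion. This conflicts with Table 7 and with the stated purpose of follow-up.

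The windows are firm for women dosed on schedule. The number of women affected is not known. The Step 5 figures assume equal, constant risk in both arms, count each such bleed as menses, and take no account of the exclusion, which would lower them by an amount the documents do not allow one to estimate.

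The consequence is limited to a secondary endpoint described by Kaplan-Meier medians and quartiles. The primary endpoint and the non-inferiority conclusion are unaffected. The definition should be corrected because the distortion depends on arm and the correction is cheap.

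**What to change.** 1. In Protocol 7.3.3 and 10.4.6.2 and in SAP 7.6.2, count as recovery only the first menses with onset after the end of the last dosing interval: last dose + 84 days (3-month) or + 28 days (1-month), which is Day 169 in both arms if on schedule. A woman with earlier menses stays at risk. Align Table 7 with this wording.
2. Tabulate menses with onset between the last dose and that date separately by arm, as on-treatment menses.
3. Also report time from the end of the last dosing interval. Once item 1 is in place, the last-dose origin builds in 84 against 28 event-free days, an offset of 84 − 28 = 56 days between the curves. From the end of the interval, observation to Week 40 is 281 − 169 = 112 days in both arms.

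The cost is one sentence in three places, an aligned table entry, one extra table and one extra Kaplan-Meier summary. No new data are needed, since menses onset dates are already recorded during treatment and follow-up.

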8 ASSESSMENT OF SAFETY

8.1 Adverse Events

Adverse events will be monitored from the time that the subject gives informed consent and throughout the study (see Section 3.5 for a definition of the study duration) and will be elicited by direct, nonleading questioning or by spontaneous reports. Further details for AE reporting can be found in Section 8.1.2.

8.1.1 Definition of an Adverse Event

An AE is the development of an undesirable medical condition or the deterioration of a pre-existing medical condition following or during exposure to a pharmaceutical product, whether or not considered causally related to the product. An undesirable medical condition can be symptoms (for example, nausea, chest pain), signs (for example, tachycardia, enlarged liver) or the abnormal results of an investigation (for example, laboratory findings, ECG). In clinical studies an AE can include an undesirable medical condition occurring at any time, including run in or washout periods, even if no IMP has been administered.

This definition includes events occurring from the time of the subject giving informed consent until the end of the study (as defined in Section 3.5).

8.1.2 Categorisation of Adverse Events

8.1.2.1 Intensity Classification

Adverse events will be classified as mild, moderate or severe according to the following criteria:

- **Mild:** symptoms do not alter the subject's normal functioning
- **Moderate:** symptoms produce some degree of impairment to function, but are not hazardous, uncomfortable or embarrassing to the subject
- **Severe:** symptoms definitely hazardous to wellbeing, significant impairment of function or incapacitation.

8.1.2.2 Causality Classification

The relationship of an AE to IMP administration will be classified according to the following:

- **Related:** reports including good reasons and sufficient information (for example plausible time sequence, dose response relationship, pharmacology, positive dechallenge and/or rechallenge) to assume a causal relationship with IMP administration in the sense that it is plausible, conceivable or likely.
- **Not related:** reports including good reasons and sufficient information (for example implausible time sequence and/or attributable to concurrent disease or other drugs) to rule out a causal relationship with IMP administration.

8.1.2.3 Assessment of Expectedness

The expectedness of an AE shall be determined by the sponsor according to the IB for an unapproved IMP, or the summary of product characteristics (SmPC) or package insert (PI) for an authorised medicinal product that is being used according to the terms and conditions of the marketing authorisation. If the IMP has marketing authorisations in several countries with different SmPCs or PIs, one will be selected as the reference document for assessing expectedness.

The reference document for assessing expectedness of AEs/event in this study will be the current (at time of study) triptorelin IB for triptorelin PR 3-month, and the PI (China) for triptorelin acetate PR 1-month.

8.1.2.4 Laboratory Test Abnormalities

Abnormalities in laboratory test values should only be reported as AEs if any of the following apply:

- They result in a change in IMP schedule of administration (change in dosage, delay in administration, IMP discontinuation),
- They require intervention or a diagnosis evaluation to assess the risk to the subject,
- They are considered as clinically significant by the investigator.

